7. STUDY PROCEDURES

The launch of the Study for a patient takes place after the patient meets the inclusion criteria. The decision on eligibility for the Study is made by the physician after reviewing the screening protocol, conducted in accordance with the patient evaluation form provided by the Sponsor. All physicians responsible for including patients in the Study at facilities in Poland and Germany will qualify patients according to the same screening procedure.

Qualified patients (or their legal guardian) must give informed consent to participate in the Study. Demographic and health data will be collected from project participants, which will then be entered by the investigator into an Electronic Case Report Form (eCRF).

After collecting this data, the patient will perform Test 1 (MCSD). The allowable time for a patient to perform Test 1 five times is 15 days (the first day of testing is the day of collection of informed consent, medical history, physical examination and eligibility criteria – Appendix A), with intervals of at least one day between test repetitions. Each time, on the day the patient will perform Test 1, it will be preceded by a CRS-R test. The schedule of appointments for patients qualified for Test 1 is shown in Table 1, Appendix A. Thus, after performing the presented procedure five times, the patient's state of consciousness will be described in two scales, which will be subject to further analysis performed under the direction of the Principal Investigator.

Observation for Test 1 can be considered successful when data are collected in the patient within the assumed time of 15 days according to the procedure described above. A patient's observation that fails to meet even one of the stated criteria (demographic and health data, CRS-R five times, and Test 1 five times) will not be considered fully completed.

If the diagnosis of the patient's state of consciousness obtained in Test 1 is higher than the UWS (so their condition will be at least MCS-) they will be qualified to perform Test 2. Patients who did not perform Test 1, but who had a score of at least MCS- in a previous CRS-R diagnosis prior to inclusion, may also be included in Test 2.

After completing a series of 5 measurements in Test 1 (MCSD), the patient's qualifying physician examines the patient at the final visit, according to the patient evaluation form provided by the Sponsor.

The procedure in Test 2 (CFA), for a patient qualified by a previous CRS-R diagnosis, begins with the collection of data on informed consent, medical history, physical examination and inclusion criteria – Appendix A. These will be collected on the first day after the patient enters the trial and entered by the investigator into the eCRF. Patients qualifying on the basis of Test 1 results will be able to proceed immediately to cognitive status assessment.

During the following 14 days, the patient will perform Test 2 three times at intervals of at least one day, which will be preceded each time by a MOCA and CRS-R test (Table 2, Appendix A). Thus, after the procedure outlined, the patient's level of cognitive function will be described using two scales (behavioural: CRS-R and MOCA and electronic - C-Eye X) which, in combination with the results of CRS-R, will be the subject of further analysis performed under the direction of the Principal Investigator.

After completing a series of 3 measurements in Test 2 (CFA), the patient's qualifying physician examines the patient at the final visit, according to the patient evaluation form provided by the Sponsor.

The occurrence of any adverse reaction must be reported in accordance with the rules set forth later in the protocol, reported using the Adverse Event Report Form, attached as Appendix 2 to this protocol.

8. INFORMED CONSENT

Informed consent to participate in the Study must be given by either the patient or the person legally responsible for the Study participant. The participant and/or the person responsible for the Study participant will be informed about the title of the Study, its objectives and goals, the ethics committee's approval issued, the conduct of the Study, and the possibility of withdrawing from participation in the Study at any stage.

Other information regarding the project and participation in the Study will be provided upon patient request.

Protection of personal data is ensured in accordance with Article 13 (1) and (2) of the General Data Protection Regulation of 27 April, 2016. (Hereinafter referred to as GDPR (Polish: RODO)).

The Patient Informed Consent Form for participation in the Study is attached as Appendix 1 to this protocol.

9. SCOPE OF DATA COLLECTION

For the purpose of broader analyses, the results obtained will be supplemented with the following patient demographics:

- sex,
- body height,
- body mass,
- date of birth,
- education,
- professional activity/occupation (before the event),
- smoking,
- handedness,
- information about the condition of the eye (possible visual defect and its type).

The patient health data collected will be as follows:

- nature of brain damage and etiology,
- date of injury occurrence,
- a clinical description of the brain damage created by the imaging study,
- the presence of chronic diseases before the injury,
- administered medications,
- having hearing and vision correcting devices before injury (including during ongoing examinations, all diagnostic sessions).

10. RANDOMISATION AND CODEBREAKING (if applicable)

Not applicable

11. SUBSEQUENT ASSESSMENTS

Follow-up tests are not provided for in the Study.

12. DEFINITION AND END OF STUDY

Termination of the patient's participation in the project occurs when the doctor examines the patient at the final visit, i.e. immediately after the last (fifth) measurement in Test 1– MCSD and/or the last (third) measurement in Test 2 – CFA.

13. DISCONTINUATION / WITHDRAWAL OF PARTICIPANT FROM STUDY

Each Study participant and/or Study supervisor has the right to discontinue (withdraw consent) at any time during the Study.

14. SOURCE DATA

The source documents used in the Study will consist of hospital records, including:

- medical history, previous and current medications taken,
- clinical observation sheets,
- diagnostic Imaging.

All documents will be kept at the medical facility implementing the Study with patients under conditions of confidentiality in accordance with data protection rules. In all documents related to the Study, in addition to the signed consent, a code – a unique patient identifier – will be used with respect to the Study participant, ensuring proper identification of the Study results collected and stored; in no case will data about the Study participant be described with their name.

15. DESCRIPTION OF MEDICAL DEVICE

C-Eye X is an integrated device consisting of a touchscreen computer, an eye tracker (a special infrared camera that tracks eye movements) and pre-installed software (run in 'kiosk' mode) that

includes a diagnostic module in the variant under clinical evaluation in this Study (and in it 2 proprietary diagnostic tests: Minimal Consciousness Detection (MCSD) and Cognitive Function Examination (CFA).

People with neurological dysfunctions and developmental disorders working with C-Eye X perform tasks based on multimedia content. The patient marks the content displayed on the device's screen (i.e. graphics, photos, texts) with their eyes by focusing on it. The patient's

Fig. 1 C-Eye X set used during the study

choice or selection of a particular item/object displayed on the screen is based on holding the eye in one place for a long time. The user interface of the C-Eye X system was created with the following design considerations in mind:

ease and intuitiveness of use of the system by the user - investigator, diagnostician,

[figure not shown]
no unnecessary buttons, functionalities, hindering the operation of the equipment, as well as the reliability of the diagnosis,

elements (different types of content, responses) with which, by definition, the patient interacts (through activation with the eyes) are maximally large, clear highly contrasting (in relation to the background on which they are presented), unambiguous so that a patient in a state of reduced consciousness struggling with cognitive and visual deficits can select them, mark them with the eyes.

[figure not shown]
Key assumptions about the C-Eye X system:

[figure not shown]
1. The visual fixation point (cursor) in diagnostic tests is a small grey dot with a white outline. The cursor was chosen so as not to attract the attention of the subject. It is not possible to change the cursor settings in Diagnosis.
2. Only the answers in tasks or actions performed (such as tracking) can be marked by the patient's eyes Other buttons on the screens are locked to operation by sight (e.g. commands, back button, etc.) – they can only be clicked by touch (this is done by the examiner, diagnostician).
3. The limit for taking measurements is enabled – a maximum of one measurement per day.
4. Marking the answers 'by sight' in the tasks is possible after the reading of the instruction by the lecturer has ended.
5. The time to mark items 'by sight' is constant for most tasks at 1.2 s (e.g. time to mark answers in questions about name, year of birth). In tasks where actions on the screen happen

automatically (e.g. tracking, reflex inhibition, etc.), other mechanisms are used to determine the results.

6. If no answer is given for 1 min, the task boards will automatically change to the next one. The process can be stopped by pressing pause. Screens containing instructions for the test taker require clicking the yellow 'next' arrow or entering the test result to move to the next board. They do not automatically change to the next.
7. The test taker has the option to pause tasks in both tests (button  in the middle, at the bottom of the screen) – pause allows one to temporarily stop the test (during the pause one cannot mark the content of tasks). One can continue the test by selecting the button again. If one chooses to pause and exit the test, the results will not be saved. Detail commands/sounds are read again, after the task is restarted – if a pause was selected during their playback.
8. It is not possible to cancel the selection or change the answer given.
9. Selecting the back arrow and confirming that you want to abort the test exits the test, without saving the results of the completed tasks. It is not possible to return and complete an aborted test.
10. In questions about the patient's name and year of birth, the first part of the question is read with a voiceover and the second part is read by a synthesiser. The voice of the synthesiser depends on the voices available on the device – male voices are selected first, then female voices (in the absence of male voices).

Sample screens – charts from the C-Eye X diagnostic module, presented as part of the clinical trials conducted:

It is the responsibility of researchers working with C-Eye to read the investigator's brochure that comes with the C-Eye X system. In addition, during the investigator training organised by the Sponsor, all investigators will be instructed on how to operate the C-Eye X in the context of conducting diagnostic tests (subject to clinical evaluation), as well as maintenance and safe operation of the device.

16. SAFETY REPORTING AND DEFINITIONS

16.1. Adverse Event (AE)

Any medical event that causes adverse effects in a clinical trial participant, even if there is no causal relationship with the products used in the clinical trial.

16.1.1. Adverse Device Effect (ADE)

An adverse event related to the use of an investigational medical device. This includes any adverse events resulting from inadequacies or inaccuracies in the instructions for use,

deployment, implantation, installation, handling or malfunction of the investigational medical device, as well as events resulting from use error or intentional misuse.

16.1.2. Serious Adverse Event (SAE)

A serious adverse event that results in a subject's death, life-threatening at the time of the event, the need for hospitalisation or prolongation of hospitalisation as a result of the event, permanent or significant impairment of health, or any other effect of the medicinal product that the physician, to the best of their knowledge, considers to be serious. A severe adverse event is also an event other than one that causes death, hospitalisation or severe life-threatening conditions, but which may pose an immediate threat to the Study participant or may require intervention to prevent one of the previously mentioned outcomes.

Planned hospitalisation for a pre-existing condition or a procedure required by a risk management plan, without serious deterioration of health, is not considered a serious adverse event.

16.1.3. Serious Adverse Device Effects (SADE)

- Adverse operation of the device that caused any consequences in the nature of a severe adverse event, i.e.:
- caused deaths,
- led to serious deterioration of health, by:
 - life-threatening illness or injury, or
 - permanent impairment of body structure or function, or
 - for required inpatient hospitalisation or extension of existing hospitalisation, or
 - the need for medical or surgical intervention to prevent a life-threatening illness or injury or permanent damage to a body structure or function.

This includes defects in the device that may have led to a serious adverse event if:

- appropriate action has not been taken, or
- no intervention was made, or
- had the circumstances been less fortunate.

16.1.4. Unanticipated Adverse Device Effect (UADE)

Means any adverse effect on health or safety caused by or related to the device, if this effect or hazard was not previously recognised in terms of its nature, severity or degree of occurrence in the test plan, as well as any other unforeseen problem related to the device that relates to the rights, safety or well-being of the participants.

An event is considered anticipated if an effect that by its nature, incidence, severity or outcome has been previously identified in a risk analysis report.

16.1.5. Serious Unanticipated Adverse Device Effect (SUADE)

A device-related serious adverse effect that, due to its nature, incidence, severity or consequences, is not identified in the current version of the risk analysis report.

16.2. Reporting of AE

The occurrence of any adverse events will be reported within 24 hours simultaneously at two levels:

- 1) to the person representing the facility where the research is being conducted (the details of this person, along with their email, phone number and fax address, will be included in the contract with the facility)

and

- 2) to [name] - an employee of AssisTech Sp. z o.o (email: [contact], [contact] address: AssisTech Sp. z o.o. [name]).

The form for reporting an adverse event is attached as Appendix 2 to this protocol..

16.3. Annual Reports

Investigators will be required to submit Study reports to AssisTech Sp. z o.o. and the Principal Investigator upon completion of the Study.

17. STATISTICS

Statistical analysis in the project will be carried out by biostatistics specialists participating on behalf of an external CRO working with the Sponsor on this Study.

17.1. Description of Statistical Methods

Nominal and ordinal scale data will be presented as counts (N) and percentages (%) in each of the categories analysed, with the denominator used to determine the percentages given.

The range of summaries for interval scale variables, in each of the categories analysed, will include: mean with standard deviation, median and lower and upper quartile, maximum and minimum value, as well as the number of people for whom estimates of basic statistics were made.

If graphical presentation of the data is necessary, box-plots (median, quartiles, range of outliers or minimum/maximum values) and/or graphs of averages with 95% confidence intervals will be used.

The distribution of the variables will be evaluated based on the quantile-quantile (Q-Q) plot and the results of the Shapiro-Wilk test. Homogeneity of variance will be assessed using Levene's test.

For the CRS-R and MOCA tests, and the C-Eye X MCSD and CFA tests, the results will be presented as:

- 1) the sum of scores for all subscales of the test,
- 2) the point value obtained in each subscale,
- 3) the percentage of the total score for all subscales of the test related to the maximum value possible for the test (23 points for the CRS- R test, 30 points for the MOCA test, 11 points for the MCSD test, 24 points for the CFA test),
- 4) the percentage value in each subscale related to the maximum value possible in the subscale.

In each subsequent visit following visit 1, the relative percentage increases in total and subscale scores will be shown for visit 1. In addition, from all consecutive visits, the sum total of the test and subscale scores for each test will be determined; the data will be presented as raw values (points) and percentages related to the sum total of the maximum possible value for the test/subscale.

Analysis of the results of each test over time (in 3 or 5 consecutive visits) will be carried out using analysis of variance with repeated measures and contrast analysis (for raw or transformed data) or Friedman analysis of variance – depending on the type of data distribution, for both raw data and transformed percentages.

For patients enrolled in Test 1, the percentages of total scores for all subscales of the test relative to the maximum value possible in the test will be used to compare the scores during the

follow-up period (in 5 consecutive visits) obtained by the MCSD C-Eye X test with those of the CRS-R test. The analysis will be conducted using one-way analysis of variance (the type of test will be a factor) with repeated measures and contrast analysis. If the assumptions of normality of distribution are not met, an appropriate nonparametric method or logarithmic transformation or aligned rank transformation will be used. The relative percentage increases in total scores at the last visit relative to the Visit 1 and the summed (from all measurements over time) total scores relative to the summed maximum possible on a given test (%) will be compared using Student's t-test or Mann-Whitney U-test, depending on the type of data distribution.

For patients enrolled in Test 2, the percentages of total scores for all subscales of the test related to the maximum value possible in the test will be used to compare the results during the follow-up period (in 3 consecutive visits) obtained with the CFA C-Eye X test with the results of the CRS-R and MOCA tests. The analysis will be conducted using one-way analysis of variance (the type of test will be a factor) with repeated measures and contrast analysis. If the assumptions of normality of distribution are not met, an appropriate nonparametric method or logarithmic transformation or aligned rank transformation will be used. Relative percentage increases in total scores at the most recent visit relative to the Visit 1 and the summed (from all measurements over time) total scores relative to the summed maximum possible on a given test (%) will be compared using one-factor analysis of variance (the type of test will be a factor) with Tukey's post-hoc test or Kruskal-Wallis one-factor analysis of variance, with multiple comparisons tests of mean ranks for all samples, depending on the type of data distribution.

Passing-Bablok orthogonal regression will be used to evaluate the consistency of test scores (summed percentages of total scores for all subscales of the test related to the maximum possible value for the test) of the MCSD and CFA C-Eye X with the CRS-R and MOCA tests. In addition, Pearson's linear correlation coefficient or Spearman's rank coefficient will be determined depending on the distribution of the data. If the assumptions of normality of distribution are not met, an appropriate nonparametric method or logarithmic transformation will be used.

The selection of appropriate methods will be discussed further in the Statistical Analysis Plan.

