17.5. Procedures for Reporting any Deviation(s) from the Original Statistical Plan

Not applicable

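### Section 17.1 lets a normality check of the variables choose how C-Eye X is compared with CRS-R and MOCA in the same patients, and its tests for summed scores and relative increases ignore the pairing

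*Protocol*

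**What the plan says.** Section 17.1 sets the check: "The distribution of the variables will be evaluated based on the quantile-quantile (Q-Q) plot and the results of the Shapiro-Wilk test". Its outcome then selects a method in these places:

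- **One instrument over time:** repeated-measures ANOVA, "or Friedman analysis of variance – depending on the type of data distribution, for both raw data and transformed percentages".
- **C-Eye X against the scales over visits (Tests 1 and 2):** repeated-measures ANOVA with type of test as factor. "If the assumptions of normality of distribution are not met, an appropriate nonparametric method or logarithmic transformation or aligned rank transformation will be used".
- **Test 1, relative increases and summed percentages:** these "will be compared using Student's t-test or Mann-Whitney U-test, depending on the type of data distribution".
- **Test 2, the same quantities with three instruments:** one-factor ANOVA "with Tukey's post-hoc test or Kruskal-Wallis one-factor analysis of variance, with multiple comparisons tests of mean ranks for all samples", again depending on the distribution.
- **Correlation:** "Pearson's linear correlation coefficient or Spearman's rank coefficient will be determined depending on the distribution of the data".

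Passing-Bablok regression is named outright for consistency. Section 17.1 ends by leaving further discussion of method selection to the SAP.

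The scores are paired by design. Section 7 says of Test 1: "Each time, on the day the patient will perform Test 1, it will be preceded by a CRS-R test". In Test 2, CRS-R and MOCA likewise precede each CFA measurement. Section 4.1 makes the difference between behavioural and C-Eye X results the secondary endpoint and says that percentage scores will be compared to show discrepancies.

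**The concern.** **The data choose the hypothesis.** A mean-based method estimates a gap in percentage points, which is what section 4.1 describes. A rank-based method asks a different question, and a log transformation a third (a ratio). When a preliminary test decides among them, the hypothesis is known only after the scores are seen. In the repeated-measures step, even a failed check leaves three options and no rule for choosing.

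**The check does not name the relevant quantity.** For a comparison within patients, the normality that matters is that of model residuals or within-patient differences. The population mixes UWS and MCS patients, and the scales are coarse (maxima 11, 24, 23 and 30). The scores can therefore look non-normal when the differences do not, and the reverse.

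**Pairing is lost.** Student's t and Mann-Whitney, one-factor ANOVA and Kruskal-Wallis treat the instruments as if they had been applied to separate groups of patients. Whichever branch the check selects, between-patient variation stays in the error term. A real discrepancy between C-Eye X and the behavioural scales could then go undetected.

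**Working it through.** The protocol states no SD, effect size or power, and section 17.2 says the sample size was not derived statistically. There is no planned figure to reproduce.

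**Inputs from the protocol:** n = 45 per test; two-sided alpha 0.05; same-patient scores.

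**Assumed inputs:** between-patient SD about 20 percentage points; within-patient error SD e = 10 or 20 per instrument; true gap 0 or 6 points.

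**1. Cost of ignoring the pairing (normal scores, approximate formulas)**

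- SD of one score: √(20² + e²) = 22.36 (e = 10) or 28.28 (e = 20).
- Correlation between instruments: 400/(400 + e²) = 0.80 or 0.50.
- SE used by the unpaired t-test: SD × √(2/45) = 4.71 or 5.96.
- Actual SE of the mean difference: e√2/√45 = 2.11 or 4.22.
- Ratio: 1/√(1 − correlation) = 2.24 or 1.41.
- Unpaired rejection threshold: 1.987 × 4.714 = 9.37, or 1.987 × 5.963 = 11.85 points.
- Rejection under no difference: P(|Z| > 9.37/2.11 = 4.44), below 0.01%; or P(|Z| > 11.85/4.22 = 2.81) = 0.5%. Nominal is 5%.
- Power for a 6-point gap, unpaired: P(Z > (9.37 − 6)/2.11 = 1.60) = 0.055; or P(Z > (11.85 − 6)/4.22 = 1.39) = 0.083.
- Power for a 6-point gap, paired t (noncentrality 6/2.108 = 2.85 or 6/4.216 = 1.42, 44 df): 0.79 or 0.29.

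Simulation (4,000 runs per scenario) applied the planned rule in full: Mann-Whitney if either score failed Shapiro-Wilk, otherwise the unpaired t-test.

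| Patient distribution | e | Planned rule, gap 0 | Planned rule, gap 6 | Paired t, gap 6 |
|---|---|---|---|---|
| Normal | 10 | 0.000 | 0.074 | 0.790 |
| Normal | 20 | 0.005 | 0.087 | 0.276 |
| Skewed | 10 | 0.001 | 0.220 | 0.788 |
| Skewed | 20 | 0.011 | 0.108 | 0.270 |
| Two clusters | 10 | 0.000 | 0.063 | 0.798 |
| Two clusters | 20 | 0.007 | 0.079 | 0.284 |

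The paired t-test rejected in 4.8% to 5.4% of runs at gap 0.

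**2. Does the object of the check matter?** In the same runs, a check on the two scores and a check on their difference gave different verdicts in about 13% of samples with normal scores, 46% to 84% with skewed scores and 15% to 78% with two clusters. If paired tests (t or signed-rank) are used either way, moving the check changed the final significance verdict in only 0.4% to 3.9% of runs.

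**3. Do the branches test different things?** With skewed differences and a true mean difference of 0, the paired t-test rejected in 6.4% of runs and the signed-rank test in 21.1%, because the median difference is not zero. A check on the differences led to 21.1% as well. Moving the check therefore does not cure the selection; only fixing the method does.

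**4. Coarse scales.** For normal scores rounded to 0–11 (SD 2) and 0–23 (SD 4) with correlation 0.6, Shapiro-Wilk rejected single-visit MCSD scores in about 30% of samples and the paired percentage difference in about 6%. For MCSD scores summed over five visits (0–55; between-visit correlation assumed 0.5 to 0.9) rejection fell to 4% to 5%, so this effect concerns single-visit scores only.

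**The case against.** The strongest reply is that section 17.1 defers method selection to the SAP, and that the quantity on which normality is checked is ordinary SAP detail. The fallback sentence follows directly on a repeated-measures ANOVA, so its normality assumption can be read as that of the model. This stands in part: the protocol does not say that raw scores are checked, and it does not exclude residuals. A reader might infer that every comparison is governed by a check on the wrong quantity, but the text does not support that. Passing-Bablok is pre-named. For Pearson or Spearman, and for the unpaired tests as written, the variables are a natural object to check. The point about the quantity fits the repeated-measures steps best.

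Other tempting readings also go too far:

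- **A score-by-score rule.** Nothing says that each visit's score is tested separately, so a chance of 1 − 0.95^10 = 40% that at least one of ten Test 1 scores fails describes no stated rule. It also assumes independence between repeated scores on the same patients.
- **Frequent reversals between a paired t-test and a sign or Friedman test.** Friedman is named only for one instrument over time, and paired t and sign tests are named nowhere. Such disagreement rates do not describe the plan's own branches.
- **A claim that C-Eye X scores higher turns on the branch.** The protocol states no rule for declaring it higher.

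The deferral does not remove the core. The switch, its branches, the unranked fallbacks and the unpaired tests are stated in the protocol itself; they are not gaps left for the SAP.

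**Conclusion.** The concern holds in this form: for same-patient comparisons, section 17.1 makes the method, and with it the hypothesis for the secondary endpoint, depend on a preliminary normality check. It leaves three unranked fallbacks in the repeated-measures step and uses tests that ignore the pairing for summed scores and relative increases.

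The lost pairing carries most of the cost. At a within-patient error SD of 10 points, power for a 6-point gap falls from about 0.79 to between 0.06 and 0.22; at 20 points, from 0.27–0.28 to between 0.08 and 0.11. The planned tests err on the conservative side, so the risk is missed differences, not false ones. The object of the check matters less, since moving it alone rarely changes a verdict.

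The sizes rest on assumed SDs, a positive correlation between instruments and a two-instrument comparison. The direction holds whenever the instruments are positively correlated within patients. The point should be corrected before analysis, but it does not affect the data being collected.

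**What to change.** In section 17.1:

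1. Remove the normality switch for the instrument comparisons.
2. Pre-specify one paired analysis: the within-patient difference in percentage score, per visit and summed over visits, reported as a mean difference with a patient-level 95% CI from a bootstrap or a paired/repeated-measures model. This replaces the unpaired tests; the comparison of relative increases should be paired in the same way.
3. Show a paired rank-based result as a sensitivity analysis only.
4. Use Q-Q plots of differences or residuals as diagnostics, with no role in choosing the method.
5. Name one correlation coefficient for all instrument pairs, for example Spearman, so that the values can be compared.

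If a sign-flip permutation p-value is added, state that it assumes symmetric differences under the null. With exponential mean-zero differences and n = 45 it rejected in 7.1% of runs, so the interval should lead.

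The cost is wording in 17.1 and the SAP and a few lines of code, with no new data. Separately, and as a minor matter, section 17.5 answers "Not applicable" on reporting deviations from the statistical plan; a sentence requiring any change of method to be reported with its reason would serve better.
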